11.3 ATO AND ASSOCIATED TREATMENTS

11.3.1 Arsenic trioxide therapy

Derivation

Derived variables	Definition
Time from diagnosis of cGvHD to first infusion of ATO (in days) The same derivation will be applied for each ATO infusion	Date of Cycle 1 onset – GvHD assessment date + 1 Missing if one of the two dates is missing
Time from starting Prednisone to first infusion of ATO (in days)	Date of Cycle 1 onset – Date of Prednisone onset +1 Missing if one of the two dates is missing
Number of cycles	1, if a date of cycle 1 onset is known 2, if a date of cycle 2 onset is known Missing otherwise
Total dose during Wi Calculated at Wi={W1, W2, W3, W4} of each cycle	For the considered period (Wi), sum of each dose took Example: C1_D1+C1_D2+C1_D3+C1_D5 for the first week
Daily dose during Wi Calculated at Wi={W1, W2, W3, W4} of each cycle	For the considered week, the daily dose will be calculated as follows: Total dose / Number of days with intake treatment during Wi
Time from the first infusion of ATO to the first day of the second cycle (in days)	Date of Cycle 2 onset – Date of Cycle 1 +1 Missing if one of the two dates is missing
Temporary discontinuation of ATO	Yes, if at least one missing infusion during the cycle 1 or cycle 2 if initiated

	No, if the patient has received all the planned doses
--	---

The following table will be presented:

Variable	Statistics / Modality	Safety Population (N = XX)
Time from diagnosis of cGvHD to first infusion of ATO (in days)	N (N Missing) Mean ± SD Median [Min ; Max]	XX (XX) XX.X ± XX.X XX [XX ; XX]
Time from diagnosis of cGvHD to second infusion of ATO (in days)	N (N Missing) Mean ± SD Median [Min ; Max]	XX (XX) XX.X ± XX.X XX [XX ; XX]
...
Time from diagnosis of cGvHD to last infusion of ATO (in days)	N (N Missing) Mean ± SD Median [Min ; Max]	XX (XX) XX.X ± XX.X XX [XX ; XX]
Time from starting Prednisone to first infusion of ATO (in days)	N (N Missing) Mean ± SD Median [Min ; Max]	XX (XX) XX.X ± XX.X XX [XX ; XX]
Number of cycles	1 2 Missing	n/N (XX.X%) n/N (XX.X%) n
First cycle		
Number of infusions	N (N Missing) Mean ± SD Median [Min ; Max]	XX (XX) XX.X ± XX.X XX [XX ; XX]
Number of weeks	N (N Missing) Mean ± SD Median [Min ; Max]	XX (XX) XX.X ± XX.X XX [XX ; XX]
Week 1		
Daily dose during W1	N (N Missing) Mean ± SD Median [Min ; Max]	XX (XX) XX.X ± XX.X XX [XX ; XX]
Number of days during W1	N (N Missing) Mean ± SD Median [Min ; Max]	XX (XX) XX.X ± XX.X XX [XX ; XX]
Total dose during W1	N (N Missing) Mean ± SD	XX (XX) XX.X ± XX.X

	Median [Min ; Max]	XX [XX ; XX]
Week 2		
Daily dose during W2	N (N Missing) Mean ± SD Median [Min ; Max]	XX (XX) XX.X ± XX.X XX [XX ; XX]
Number of days during W2	N (N Missing) Mean ± SD Median [Min ; Max]	XX (XX) XX.X ± XX.X XX [XX ; XX]
Total dose during W2	N (N Missing) Mean ± SD Median [Min ; Max]	XX (XX) XX.X ± XX.X XX [XX ; XX]
Week 3		
Daily dose during W3	N (N Missing) Mean ± SD Median [Min ; Max]	XX (XX) XX.X ± XX.X XX [XX ; XX]
Number of days during W3	N (N Missing) Mean ± SD Median [Min ; Max]	XX (XX) XX.X ± XX.X XX [XX ; XX]
Total dose during W3	N (N Missing) Mean ± SD Median [Min ; Max]	XX (XX) XX.X ± XX.X XX [XX ; XX]
Week 4		
Daily dose during W4	N (N Missing) Mean ± SD Median [Min ; Max]	XX (XX) XX.X ± XX.X XX [XX ; XX]
Number of days during W4	N (N Missing) Mean ± SD Median [Min ; Max]	XX (XX) XX.X ± XX.X XX [XX ; XX]
Total dose during W4	N (N Missing) Mean ± SD Median [Min ; Max]	XX (XX) XX.X ± XX.X XX [XX ; XX]
Temporary discontinuation of ATO*	No Yes Missing	n/N (XX.X%) n/N (XX.X%) n
Second cycle		
Patients who entered into the 2 nd cycle	No Yes Missing	n/N (XX.X%) n/N (XX.X%) n
Time from the first infusion of ATO to the first day of the second cycle (in days)	N (N Missing) Mean ± SD Median [Min ; Max]	XX (XX) XX.X ± XX.X XX [XX ; XX]
Number of infusions	N (N Missing) Mean ± SD Median [Min ; Max]	XX (XX) XX.X ± XX.X XX [XX ; XX]

Week 1		
Daily dose during W1	N (N Missing) Mean ± SD Median [Min ; Max]	XX (XX) XX.X ± XX.X XX [XX ; XX]
Number of days during W1	N (N Missing) Mean ± SD Median [Min ; Max]	XX (XX) XX.X ± XX.X XX [XX ; XX]
Total dose during W1	N (N Missing) Mean ± SD Median [Min ; Max]	XX (XX) XX.X ± XX.X XX [XX ; XX]
Week 2		
Daily dose during W2	N (N Missing) Mean ± SD Median [Min ; Max]	XX (XX) XX.X ± XX.X XX [XX ; XX]
Number of days during W2	N (N Missing) Mean ± SD Median [Min ; Max]	XX (XX) XX.X ± XX.X XX [XX ; XX]
Total dose during W2	N (N Missing) Mean ± SD Median [Min ; Max]	XX (XX) XX.X ± XX.X XX [XX ; XX]
Week 3		
Daily dose during W3	N (N Missing) Mean ± SD Median [Min ; Max]	XX (XX) XX.X ± XX.X XX [XX ; XX]
Number of days during W3	N (N Missing) Mean ± SD Median [Min ; Max]	XX (XX) XX.X ± XX.X XX [XX ; XX]
Total dose during W3	N (N Missing) Mean ± SD Median [Min ; Max]	XX (XX) XX.X ± XX.X XX [XX ; XX]
Week 4		
Daily dose during W4	N (N Missing) Mean ± SD Median [Min ; Max]	XX (XX) XX.X ± XX.X XX [XX ; XX]
Number of days during W4	N (N Missing) Mean ± SD Median [Min ; Max]	XX (XX) XX.X ± XX.X XX [XX ; XX]
Total dose during W4	N (N Missing) Mean ± SD Median [Min ; Max]	XX (XX) XX.X ± XX.X XX [XX ; XX]
Temporary discontinuation of ATO	No Yes Missing	n/N (XX.XX%) n/N (XX.XX%) n

In case of temporary discontinuation of ATO, a listing will be provided.

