### **7.3.2 Treatment plan**

#### ***7.3.2.1 Arsenic trioxide therapy***

As soon as the diagnosis of chronic GvHD requiring systemic immunosuppressive therapy is confirmed, patients will receive in addition to cyclosporine A (if relevant) and corticosteroids 1 mg/kg/day, ATO 0,15 mg/kg/day over a 4 weeks period (one cycle).

The treatment plan is indicative, but it is important to respect the number of 11 perfusions per cycle. In the case of a temporary discontinuation of ATO therapy for medical or other reasons, the canceled infusions will be scheduled as soon as possible.

- Week 1: day 1 to 5
- Week 2: 3 times per week (example: day 8, 10 and 12)
- Week 3: 2 times per week (example: day 15 and 17)
- Week 4: 1 time per week (example: day 24)

ATO should be administered within 10 days of starting prednisone 1mg/kg/day. Follow-up dates for response assessment and laboratory tests relate to the date of ATO infusion. Patients in partial response after the 1st cycle of ATO will be eligible to receive a second cycle of ATO as consolidation therapy. A delay of 8 weeks to a maximum of 11 weeks (from the first infusion of ATO) will be observed between the two cycles of ATO therapy.

Response definition is as follows:

- Complete remission (CR) is defined as complete disappearance of any sign of chronic GvHD
- Partial remission (PR) is defined as improvement of 1 or more point on a 4 to 7-point scale or an improvement of 2 or more points on a 10 to 12-points scale in at least 1 organ or site without progression in any other organ or site. For patients with BOS, an absolute improvement in %FEV1 of 10% predicted or more (eg, 50% to 60%) is considered a PR as long as the initial % FEV1 is < 70%. Normalization ( $\geq 80\%$ ) is considered a CR.
- Progressive disease (PD) is defined as at least one organ system has worsened by at least one stage without improvement of any other organ systems from baseline:
  - For skin, eye, esophagus, and upper and lower gastro-intestinal (GI) tract, a worsening of 1 point or more on the 0 to 3 scale is considered progression, except a change from 0 to 1, which is considered trivial progression since it often reflects mild, nonspecific, intermittent, self-limited symptoms and signs that do not warrant a change of therapy.

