**Figure 1. Study plan of investigational product and secondary systemic treatment**

### Dose delay, modification and reinitiation

Treatment with ATO must be interrupted, adjusted, or discontinued before the scheduled end of therapy at any time that a toxicity grade 3 or greater, on the National Cancer Institute Common Toxicity Criteria, is observed and judged to be possibly related to ATO treatment. Patients who experience such reactions that are considered ATO related must resume treatment only after resolution of the toxic event or after recovery to baseline status of the abnormality that prompted the interruption. In such cases, treatment must resume at 50% of the previous daily dose. If the toxic event does not recur within 3 days of restarting treatment at the reduced dose, the daily dose can be escalated back to 100% of the original dose. Patients who experience a recurrence of toxicity must be removed from treatment.

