11.2.2 Baseline characteristics

Derivation

Derived variable	Definition
Time from transplant to chronic GVHD (in days)	Assessment date - Date of the first allogeneic stem cell transplantation +1
Daily steroid dose (Prednisone): mg/kg/d	Considering the treatment line when the baseline occurs, the daily dose is calculated as: Dose*frequency/weight The frequency can be: once a day, twice a day, 1 day on 2 etc.
Daily cyclosporine dose	Considering the treatment line when the baseline occurs, the daily dose is calculated as: Dose*frequency The frequency can be: once a day, twice a day, 1 day on 2 etc.

The following table will be presented:

Variable	Statistics / Modality	Safety Population (N = XX)
Significant current disease	No	n/N (XX.X%)
	Yes	n/N (XX.X%)
	Missing	n
Donor / Recipient features	Modality 1	n/N (XX.X%)
	Modality 2	n/N (XX.X%)

	Modality n	n/N (XX.X%)
	Missing	n
Conditioning regimen		
Conditioning regimen	Modality 1	n/N (XX.X%)
	Modality 2	n/N (XX.X%)

	Modality n	n/N (XX.X%)
	Missing	n
Previous infusion of DLI		
DLI	No	n/N (XX.X%)
	Yes	n/N (XX.X%)
	Missing	n
Time from transplant to GVHD		
Time from transplant to chronic GVHD (in days)	N (N Missing)	XX (XX)
	Mean ± SD	XX.X ± XX.X
	Median [Min ; Max]	XX [XX ; XX]
Concomitant disease		
Current disease?	No	n/N (XX.X%)
	Yes	n/N (XX.X%)
	Missing	n
Haematology		
Leucocytes	N (N Missing)	XX (XX)
	Mean ± SD	X.XX ± X.XX
	Median [Min ; Max]	X.X [X.X ; X.X]
Neutrophils	N (N Missing)	XX (XX)
	Mean ± SD	X.XX ± X.XX
	Median [Min ; Max]	X.X [X.X ; X.X]
Lymphocytes	N (N Missing)	XX (XX)
	Mean ± SD	X.XX ± X.XX
	Median [Min ; Max]	X.X [X.X ; X.X]

Monocytes	N (N Missing) Mean ± SD Median [Min ; Max]	XX (XX) X.XX ± X.XX X.X [X.X ; X.X]
Eosinophils	N (N Missing) Mean ± SD Median [Min ; Max]	XX (XX) X.XX ± X.XX X.X [X.X ; X.X]
Hemoglobin	N (N Missing) Mean ± SD Median [Min ; Max]	XX (XX) XX.XX ± XX.XX XX.X [XX.X ; XX.X]
Platelets	N (N Missing) Mean ± SD Median [Min ; Max]	XX (XX) XXX.X ± XXX.X XXX [XXX ; XXX]
aPTT	N (N Missing) Mean ± SD Median [Min ; Max]	XX (XX) XX.X ± XX.X XX [XX ; XX]
Serum chemistries		
Creatinine	N (N Missing) Mean ± SD Median [Min ; Max]	XX (XX) XX.XX ± XX.XX XX.X [XX.X ; XX.X]
Uric acid	N (N Missing) Mean ± SD Median [Min ; Max]	XX (XX) XXX.X ± XXX.X XXX [XXX ; XXX]
Total bilirubin	N (N Missing) Mean ± SD Median [Min ; Max]	XX (XX) XX.XX ± XX.XX XX.X [XX.X ; XX.X]
Alkaline phosphatases	N (N Missing) Mean ± SD Median [Min ; Max]	XX (XX) XXX.X ± XXX.X XXX [XXX ; XXX]

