11.3.2 Associated treatment

- **Prednisone and Ciclosporin A**

Derivation

Derived variables	Definition
Time from diagnosis of cGvHD to Prednisone onset (in days)	Date of Prednisone onset – GvHD assessment date +1 Missing if one of the two dates is missing
Time from diagnosis of cGvHD to Ciclosporin onset (in days)	Date of Ciclosporin onset – GvHD assessment date +1 Missing if one of the two dates is missing
Treatment duration (in days) Calculated for Prednisone and Ciclosporin	Last treatment line end date – First treatment line start date +1 Missing if one of the two dates is missing
Daily dose for Prednisone and Ciclosporin Calculated for Prednisone (mg/kg/d) and Ciclosporin (mg/d) separately	First, for each treatment line, the total dose will be calculated as follows: dose*frequency*number of days The frequency can be: once a day, twice a day, 1 day on 2 etc. The average daily dose is then defined as follows: Sum of each dose treatment line / Treatment duration
Reason of change	As the treatment of a same patient can be changed several times, if a reason of change is met more than once, it will only be counted as one reason. Thus, the denominator will be the same as the analysis population (i.e. Safety Population)

Secondary immunosuppressive treatment after first ATO infusion	No, if no treatment intake Yes, if at least one treatment intake
--	---

The following table will be presented:

Variable	Statistics / Modality	Safety Population (N = XX)
Prednisone		
Time from diagnosis of cGvHD to first Prednisone dose (in days)	N (N Missing) Mean ± SD Median [Min ; Max]	XX (XX) XX.X ± XX.X XX [XX ; XX]
Treatment duration (in days)	N (N Missing) Mean ± SD Median [Min ; Max]	XX (XX) XX.X ± XX.X XX [XX ; XX]
Daily dose (mg/kg/d)	N (N Missing) Mean ± SD Median [Min ; Max]	XX (XX) XX.X ± XX.X XX [XX ; XX]
Number of changes	N (N Missing) Mean ± SD Median [Min ; Max]	XX (XX) XX.X ± XX.X XX [XX ; XX]
Reason of change	Reason 1 Reason 2 ... Reason n	n/N (XX.X%) n/N (XX.X%) ... n/N (XX.X%)
Ciclosporin		
Ciclosporin intake	No Yes Missing	n/N (XX.X%) n/N (XX.X%) n
Time from diagnosis of cGvHD to first Ciclosporin dose (in days)	N (N Missing) Mean ± SD Median [Min ; Max]	XX (XX) XX.X ± XX.X XX [XX ; XX]
Treatment duration (in days)	N (N Missing) Mean ± SD Median [Min ; Max]	XX (XX) XX.X ± XX.X XX [XX ; XX]
Daily dose (mg/d)	N (N Missing) Mean ± SD Median [Min ; Max]	XX (XX) XX.X ± XX.X XX [XX ; XX]

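### Two SAP exposure derivations give wrong descriptive results: the temporary-discontinuation flag misses ATO interruptions that were made up, and the average prednisone dose labelled mg/kg/d has no weight term

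*SAP*

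**What the plan says.** **ATO interruption.** SAP 11.3.1 derives temporary discontinuation of ATO from two rules: "Yes, if at least one missing infusion during the cycle 1 or cycle 2 if initiated" and "No, if the patient has received all the planned doses". Neither refers to dates or delay. The section ends by promising a listing when there has been a temporary discontinuation. Protocol 7.3.2.1 calls the calendar indicative, stresses the count of 11 infusions per cycle, and states: "In the case of a temporary discontinuation of ATO therapy for medical or other reasons, the canceled infusions will be scheduled as soon as possible".

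**ATO dose.** SAP 11.3.1 reports a total dose for each of weeks W1 to W4, and a daily dose equal to that total divided by the number of days with an infusion. No unit is given and weight does not enter. The week-1 illustration reads "Example: C1_D1+C1_D2+C1_D3+C1_D5 for the first week". The protocol prescribes ATO per kg and, in its section on dose delay, modification and reinitiation, says that after an ATO-related toxicity "treatment must resume at 50% of the previous daily dose".

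**Prednisone.** SAP 11.3.2 builds the average thus: "First, for each treatment line, the total dose will be calculated as follows: dose*frequency*number of days". It then divides the sum over treatment lines by treatment duration and labels the result mg/kg/d. SAP 11.2.2 defines "Daily steroid dose (Prednisone): mg/kg/d" as dose times frequency divided by weight, and SAP 11.4.2.3 uses the same division at each visit.

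**The concern.** In the protocol, a temporary discontinuation is a pause followed by catch-up. The SAP variable of that name tests only whether the final count is short. The patient it is named for is therefore coded No, and the patient who stopped permanently is coded Yes. If the listing is driven by the flag, it would omit the made-up interruptions and show the permanent stops.

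For prednisone, one recorded dose is processed in three places and divided by weight in only two. All three results are presented as mg/kg/d, and they cannot all be right.

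At stake is the description of how well the 11-infusion schedule was delivered and how much steroid was given alongside it. Tolerability is a secondary endpoint, so a reader will look to these tables.

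**Working it through.** **1. Reference count.** Infusions per cycle (Protocol 7.3.2.1; SAP 9.3.3): 5 + 3 + 2 + 1 = 11. This reproduces the stated 11.

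**2. The flag applied as written.**

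| Patient | Infusions given | SAP flag |
|---|---|---|
| Never interrupted | 11 | No |
| Interrupted, then made up | 11 | No |
| Stopped for good after 7 | 7 | Yes |

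The flag cannot separate the first two patients and labels the third as temporary. If a missing infusion is instead read as one missed on its planned date, the second patient meets the Yes rule and the No rule at once. The definition fails on either reading.

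**3. Prednisone average.** SAP 11.3.2 formula: sum of (dose × frequency × days) / duration.

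- Constant dose of 0.5 mg/kg/d at an assumed 70 kg: 0.5 × 70 = 35 mg a day, so the average is 35, printed as mg/kg/d.
- Illustrative course (an assumption) of 14 days each at 1.0, 0.75, 0.65 and 0.5 mg/kg/d: (1.0 + 0.75 + 0.65 + 0.5) / 4 = 0.725 mg/kg/d. The SAP formula gives 0.725 × 50 = 36.25 at 50 kg, 50.75 at 70 kg and 72.5 at 100 kg. Divided by weight, it is 0.725 at every weight.

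This assumes that doses are recorded in mg. The other sections imply it: if the record were already in mg/kg, dividing again in 11.4.2.3 would turn 1 mg/kg/d at 50 kg into 1 / 50 = 0.02, and every patient on up to that dose would fall into the lowest dose band there (up to 0.25).

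**4. Half-doses.** For an assumed 80 kg patient, a full infusion is 0.15 × 80 = 12 mg and a full week 1 is 5 × 12 = 60 mg. With two of the five halved, the total is 3 × 12 + 2 × 6 = 48 mg and the daily dose 48 / 5 = 9.6 mg. The table therefore moves. But if the unit is mg, 9.6 mg is also the full dose at 9.6 / 0.15 = 64 kg, and a half dose at 100 kg (0.5 × 0.15 × 100 = 7.5 mg) equals a full dose at 50 kg (0.15 × 50 = 7.5 mg). Nothing marks the value as a reduction.

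**5. What a week means.** Assume a 14-day pause after day 5. The infusions then fall on days 1–5, 22, 24, 26, 29, 31 and 38. If W1–W4 are calendar weeks, they hold 8 of 11 infusions (73%). If they follow planned-infusion labels, they hold all 11. The SAP does not say which applies.

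**6. The week-1 example.** It names 4 of 5 daily infusions; day 4 is absent. Followed literally, it would capture 4/5 = 80% of the week's dose.

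**The case against.** The strongest reply is that the exposure tables carry more than this flag. SAP 11.3.1 also tabulates the number of infusions, the number of weeks in cycle 1, infusion days per week, and the time from diagnosis to each infusion up to the last. The adverse-event listing in SAP 12.1 gives cycle dates, causality and the action taken. A reader might infer that interruptions vanish from the report, or that the flag is the trial's only measure of deliverability; the documents do not support either. What remains is narrower: none of these outputs counts interrupted patients, and cycle 2 has no row for number of weeks.

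Other stronger readings also fail:

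- **Half-doses are invisible.** They are not; they lower the weekly total and daily dose (step 4). They are only not identified as reductions.
- **Weekly totals lose about a quarter of the dose after a delay.** This requires calendar weeks, which the SAP does not state.
- **Week-1 totals are 20% short.** The governing rule adds up every dose taken in the week, which includes day 4. The omission is a slip in an illustration.
- **The corticosteroid endpoint has the wrong unit.** It does not; 11.4.2.3 divides by weight.

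Two further defences stand in part. A count of infusions is worth reporting, because the protocol stresses 11, so the variable is misnamed rather than useless. And the listing sentence does not say that the derived flag selects the patients, so the omission from the listing is conditional. On prednisone, the intended unit is plain from the label, and a value such as 35 would probably be noticed. That is a reason to expect correction, not a reason to leave the formula.

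**Conclusion.** Two rules are wrong as written. The flag measures incomplete cycles under the name of temporary discontinuation: a made-up interruption counts as zero and a permanent stop counts as temporary. The prednisone average in 11.3.2 is too large by a factor equal to body weight in kg, which is 50- to 100-fold over an assumed 50–100 kg, provided doses are recorded in mg.

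The first conclusion needs no assumption beyond the wording, since both readings of a missing infusion fail. Its numerical effect cannot be stated, because the documents give no interruption rate.

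Three lesser points belong with these: dose reductions are not identified, the meaning of W1–W4 is open, and the week-1 example omits day 4.

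All of this is descriptive exposure reporting. The primary test in 11.4.1.1 and the corticosteroid results in 11.4.2.3 are untouched. Severity: minor.

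**What to change.** **SAP 11.3.1**

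- Temporary discontinuation: Yes if any infusion was cancelled or postponed, for any reason, and treatment later resumed, whether or not the count reached 11.
- Add a separate variable, cycle not completed: fewer than 11 infusions given in that cycle. Keep it descriptive; whether it also settles what a completed first cycle means for the Full Analysis Set in 11.1 should be decided separately.
- State that the listing uses the revised flag.
- Report ATO per infusion in mg/kg, and cumulative dose over all infusions of the cycle whenever they were given. Identify reductions from the recorded reason for a dose change, or against the protocol dose with a stated rounding tolerance so that rounding is not counted as a reduction.
- Say whether W1–W4 are calendar weeks or planned-infusion labels, and add C1_D4 to the example.

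**SAP 11.3.2**

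- Divide the prednisone total by body weight and name the weight: either the one used in 11.2.2, or the latest recorded weight for each treatment line. The second suits a course lasting months.

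**Cost.** SAP wording and a little programming. Protocol Table 2 already collects the date and dose of each infusion and the reason for any change. Weight is taken weekly during ATO (Protocol 8.2), and Form A has a weight field at later assessments. The number of reported interruptions may rise.

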11.3.2 Associated treatment

- **Prednisone and Ciclosporin A**

Derivation

Derived variables	Definition
Time from diagnosis of cGvHD to Prednisone onset (in days)	Date of Prednisone onset – GvHD assessment date +1 Missing if one of the two dates is missing
Time from diagnosis of cGvHD to Ciclosporin onset (in days)	Date of Ciclosporin onset – GvHD assessment date +1 Missing if one of the two dates is missing
Treatment duration (in days) Calculated for Prednisone and Ciclosporin	Last treatment line end date – First treatment line start date +1 Missing if one of the two dates is missing
Daily dose for Prednisone and Ciclosporin Calculated for Prednisone (mg/kg/d) and Ciclosporin (mg/d) separately	First, for each treatment line, the total dose will be calculated as follows: dose*frequency*number of days The frequency can be: once a day, twice a day, 1 day on 2 etc. The average daily dose is then defined as follows: Sum of each dose treatment line / Treatment duration
Reason of change	As the treatment of a same patient can be changed several times, if a reason of change is met more than once, it will only be counted as one reason. Thus, the denominator will be the same as the analysis population (i.e. Safety Population)

Secondary immunosuppressive treatment after first ATO infusion	No, if no treatment intake Yes, if at least one treatment intake
--	---

The following table will be presented:

Variable	Statistics / Modality	Safety Population (N = XX)
Prednisone		
Time from diagnosis of cGvHD to first Prednisone dose (in days)	N (N Missing) Mean ± SD Median [Min ; Max]	XX (XX) XX.X ± XX.X XX [XX ; XX]
Treatment duration (in days)	N (N Missing) Mean ± SD Median [Min ; Max]	XX (XX) XX.X ± XX.X XX [XX ; XX]
Daily dose (mg/kg/d)	N (N Missing) Mean ± SD Median [Min ; Max]	XX (XX) XX.X ± XX.X XX [XX ; XX]
Number of changes	N (N Missing) Mean ± SD Median [Min ; Max]	XX (XX) XX.X ± XX.X XX [XX ; XX]
Reason of change	Reason 1 Reason 2 ... Reason n	n/N (XX.X%) n/N (XX.X%) ... n/N (XX.X%)
Ciclosporin		
Ciclosporin intake	No Yes Missing	n/N (XX.X%) n/N (XX.X%) n
Time from diagnosis of cGvHD to first Ciclosporin dose (in days)	N (N Missing) Mean ± SD Median [Min ; Max]	XX (XX) XX.X ± XX.X XX [XX ; XX]
Treatment duration (in days)	N (N Missing) Mean ± SD Median [Min ; Max]	XX (XX) XX.X ± XX.X XX [XX ; XX]
Daily dose (mg/d)	N (N Missing) Mean ± SD Median [Min ; Max]	XX (XX) XX.X ± XX.X XX [XX ; XX]
Number of changes	N (N Missing) Mean ± SD Median [Min ; Max]	XX (XX) XX.X ± XX.X XX [XX ; XX]

Reason of change	Reason 1 Reason 2 ... Reason n	n/N (XX.X%) n/N (XX.X%) ... n/N (XX.X%)
------------------	---	--

- **Concomitant treatments**

Concomitant treatments will be presenting by descending sort of use.

The following table will be presented:

		Safety Population (N=XX)
Patients who received at least one concomitant treatment		n/N (XX.X%)
TRT 1		n/N (XX.X%)
TRT 2		n/N (XX.X%)
...		...
TRT n		n/N (XX.X%)

- **Secondary immunosuppressive treatment**

Variable	Statistics / Modality	Safety Population (N = XX)
Secondary immunosuppressive treatment	No	n/N (XX.X%)
	Yes	n/N (XX.X%)
	Missing	n

